#### 5.2.2 Sensitivity Analyses

#### 5.2.2.1 Per Protocol Population

For the PP analysis, participants who have engaged with at least one group session of the programme will be included. The PP will adhere to the same steps as the primary analysis.

#### 5.2.2.2 Intention-to-treat Population

To allow for full analysis set, missing data will be imputed using a multiple imputation procedure which substitutes predicted values from a regression equation. The imputation will be carried out by the MI command in Stata 15. MI replaces missing values with multiple sets of simulated values to complete the data, performs standard analysis on each completed dataset, and adjusts the obtained parameter estimates for missing-data uncertainty using Rubin's rules to combine estimates 16.

The following procedure will be followed:

- The MI will be set as wide
- The MI will register imputation of the average daily physical activity at 12 months and at baseline

Date:

20/03/2019

Clinical Trials Unit

A regression method will be used, where the registered variables will be individually
adjusted for the randomisation and stratification factors (sex and ethnicity), with 100
imputations to avoid biased estimates, rseed (2259) and the force options

 MI estimate will provide the final results using the same regression model as the primary analysis and covariate adjustments.

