#### 1.2.6 Sample size calculations

The primary outcome is change from baseline to 12 months average daily physical activity, as quantified by the Euclidean norm minus one (ENMO) method measured in milligravity units (mg). This is the main measure of activity derived from the activity monitor that will be used in this study (PACES). In order to detect a minimum clinically significant difference of 2.1 mg, which is equivalent to an overall increase in physical activity volume of approximately 30 minutes of light walking at 4km/h, assuming a standard deviation of 5.3 mg [1], a power of 80% and significance level of 5%, the sample size requires 202 participants. To allow for 20% loss to follow-up and 10% noncompliance of the activity monitor, we will therefore need to recruit 290 participants (145 in each group).

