## 3.3 Intention-to-treat Population/Full analysis set

The intention-to-treat (ITT) analysis population will consist of all participants randomised. Participants will be analysed in the group to which they were randomly allocated and regardless of any protocol deviations or violations. Multiple imputation methods will be used to impute missing outcome data. This will be a sensitivity analysis.

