### 5.2 Primary Endpoint Analysis

### 5.2.1 Primary Analysis of Primary Endpoints

The primary outcome is change in overall volume of physical activity (average acceleration, ENMO) from baseline to 12 months. For the primary outcome treatment arm will be compared using linear regression modelling with

- 1. a binary indicator for randomisation group as the explanatory variable
- terms for stratification factors (gender and ethnicity) as confounders
- 3. adjustment for the change from baseline in accelerometer wear time and baseline average daily physical activity.

The primary analysis at 12 months will be based on complete data.

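### The imputed ITT analysis needs a wear-time covariate that is never imputed, and it leaves baseline activity out of the imputation of 12-month activity, so it is a weak check on missing data

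*SAP*

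**What the plan says.** Section 3.3 of the SAP defines the population: "The intention-to-treat (ITT) analysis population will consist of all participants randomised". Missing outcomes are to be filled in by multiple imputation, and the result is a sensitivity analysis. Section 2.1 gives its purpose, which is to test whether the complete-case finding is robust to missing data.

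Section 5.2.2.2 fixes the method.
- Variables imputed: "The MI will register imputation of the average daily physical activity at 12 months and at baseline". No others are named.
- Predictors: the registered variables are handled one at a time and "adjusted for the randomisation and stratification factors (sex and ethnicity), with 100" imputations. Baseline activity is not listed as a predictor of 12-month activity, nor the reverse.
- Model fitted afterwards: "MI estimate will provide the final results using the same regression model as the primary analysis and covariate adjustments".

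Besides arm, gender and ethnicity, the primary model in section 5.2.1 has "adjustment for the change from baseline in accelerometer wear time and baseline average daily physical activity".

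Section 3.1 separately removes from every analysis anyone who consented but did not attend the baseline assessment.

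**The concern.** Two features of the specification do not fit its purpose.

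**Population.** Change in wear time is a covariate in the fitted model but is not imputed. A participant with no monitor record at 12 months, or at baseline, has no value for it. A regression cannot use a row with a missing covariate, so that person is dropped even though their activity was imputed. The analysis would be reported as ITT but run on something close to the complete cases.

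**Imputation model.** The analysis models change and conditions on baseline activity. The imputation draws 12-month activity without looking at the same person's baseline, so imputed values are unrelated to it within arm, sex and ethnicity. The imputation model is narrower than the analysis model it feeds.

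The primary analysis is complete-case by design, and the per-protocol set in section 3.4 also requires complete outcomes. The plan allows for 30% of participants lacking the primary outcome, so this analysis carries most of the claim of robustness.

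**Working it through.** **Inputs from SAP section 1.2.6.** The design is to "detect a minimum clinically significant difference of 2.1 mg", "assuming a standard deviation of 5.3 mg", with "a power of 80% and significance level of 5"%. It needs 202 evaluable participants and allows for 20% loss to follow-up and 10% monitor non-compliance, giving 290 recruited (145 per arm).

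**Plan's own figure.** n per arm = 2 × (1.96 + 0.8416)² × 5.3² / 2.1² = 100 by the normal formula. The t-based calculation gives 101, so 202 in total. 202 / 0.70 = 288.6, rounded up to 289 and then to 290 for equal arms. The sample size reproduces and is not at issue.

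**Step 1: who is dropped for lack of a wear-time change.**
- Lost to follow-up: 290 × 0.20 = 58, leaving 232.
- If non-compliant wearers also have no usable wear time: 290 × 0.30 = 87, leaving 203, essentially the complete cases.
- The SAP has no rule for wear time that is recorded but insufficient, so the number dropped lies between 58 and about 87.

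**Step 2: if wear time is resolved, what does omitting baseline do?** Simulation with N = 290, true effect 2.1 mg, SD of change 5.3 mg and about 30% of 12-month values missing.

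Assumptions not in the SAP: baseline/12-month correlation ρ of 0.5, 0.7 or 0.8; equal SDs at both visits; baseline fully observed; wear time left out; and the missingness mechanisms below.

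*Random loss*

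| ρ | Complete-case SE | SE, imputation as specified | Ratio |
|---|---|---|---|
| 0.5 | 0.65 | 0.72 | 1.11 |
| 0.7 | 0.69 | 0.90 | 1.30 |
| 0.8 | 0.71 | 1.06 | 1.49 |

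Repeat runs differ by about 0.01. The estimate itself is unbiased (2.13-2.15 mg in one set of runs). The fitted baseline slope shrinks by about the fraction observed: at ρ = 0.7 it is 0.70 × 0.70 = 0.49, as simulated. The actual spread of the estimate over repeated trials was 0.66/0.79/0.92, so part of the larger SE is the pooled SE overstating the true variability.

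*Loss related to baseline equally in both arms.* Estimates were 2.06-2.15 mg, so there is no bias. The SE was 0.72-1.04.

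*Loss related to baseline differently by arm.* The approximate bias is ρ × SD × d. Here SD = 5.3 / √(2(1 − ρ)), and d is the between-arm difference in mean baseline, in SD units, among those retained. Suppose control loss is random and, in the intervention arm, the odds of loss fall by a factor of about 0.52 per SD of baseline activity (a log odds ratio of −0.65). With 70% retained, d = 0.18.
- ρ = 0.5: SD = 5.30; 2.1 + 0.5 × 5.30 × 0.18 = 2.58 mg
- ρ = 0.7: SD = 6.84; 2.1 + 0.7 × 6.84 × 0.18 = 2.96 mg
- ρ = 0.8: SD = 8.38; 2.1 + 0.8 × 8.38 × 0.18 = 3.31 mg

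Simulation of this mechanism gave 2.56/2.99/3.30 mg, with complete-case regression at 2.09-2.11 mg.

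The size depends on the mechanism chosen. An odds ratio of about 0.67 in the intervention arm only gave 2.42/2.63/2.87 mg. A deliberately extreme case, with selection in opposite directions in the two arms, gave 3.25/4.15/5.05 mg.

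**Step 3: baseline added to the imputation model.** Across random, equal-in-both-arms and opposite-direction loss, estimates were 2.06-2.14 mg with SE 0.66-0.74, close to complete case (0.65-0.73).

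**The case against.** The strongest reply is that this is only a sensitivity analysis. Sections 2.1 and 5.2.1 fix the primary analysis as complete-case regression adjusted for baseline, and in the simulations that analysis is unbiased wherever loss depends only on baseline and arm. The primary estimate, its p-value and the sample size do not change. That stands, and it limits how serious the point is.

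Two stronger readings are tempting, and the SAP does not support either.

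- *A reader might infer that the imputed estimate is biased as such.* It is not. Under random loss, or loss related to baseline in the same way in both arms, the treatment effect is unbiased and only precision suffers. Bias needs baseline-related loss that differs by arm. That is plausible, since only the intervention arm is asked to attend two group sessions and is sent 82 text messages (section 1.2.3). But the SAP gives no dropout pattern and no baseline/12-month correlation, so the bias figures are illustrations.
- *A reader might infer that the analysis exactly repeats the complete-case result.* That holds for people with no monitor record. Someone with recorded but insufficient wear could still enter, and the SAP does not say.

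The two faults should not be added together. While missing wear time excludes people, how their activity was imputed has little effect.

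**Conclusion.** The point holds, with conditions. Sections 3.3, 5.2.1 and 5.2.2.2 cannot all be followed as written: the fitted model needs a variable that is missing for those whose outcome is imputed. Between 58 and about 87 of 290 would be dropped on the plan's own allowances.

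If wear time is resolved, omitting baseline activity makes the treatment-effect SE about 10-50% larger than complete-case regression at correlations of 0.5 to 0.8. It biases the estimate only under arm-dependent, baseline-related loss, to about 2.6-3.3 mg against 2.1 mg in the illustration. These results rest on the assumed correlations, equal SDs and missingness mechanisms.

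This should be fixed, but it does not threaten the primary analysis. It matters because it is the plan's only imputation-based check. As specified, that check is either largely redundant or less precise than the analysis it is meant to test.

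**What to change.** Revise section 5.2.2.2 as follows.

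1. Impute baseline and 12-month activity jointly, by chained equations or a multivariate normal model, each in the other's model together with arm, sex and ethnicity.
2. Either impute wear time in the same model or omit change in wear time from the pooled model. State how recorded but insufficient wear is handled.
3. Derive change in activity (and in wear time, if kept) after imputation.
4. Require the number analysed to equal the number randomised. Reconcile this with section 3.1, which removes non-attenders at baseline from all analyses and so conflicts with section 3.3 if any such person was randomised.

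Collected variables such as age, BMI, ISWT and RPAQ could be added as predictors, and a delta-adjusted run could be added to test the missing-at-random assumption. Both are optional and not needed to correct the error.

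The cost is SAP wording and a few lines of code. No new data are needed.

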#### 5.2.2.3 Stratified analyses

Interaction effects will be fitted between intervention arm and gender (male vs. female) and ethnicity (White European vs. other). If the interaction term is statistically significant at the 10% level then stratified analyses will be performed for that factor using the same model as the primary analyses.

### 5.3 Secondary Endpoint Analyses

The analyses of the secondary outcomes will be conducted in a similar manner as the main analysis using the appropriate model type, logistic regression for binary outcomes, linear for continuous and ordinal for ordinal outcome.

The assumptions of each analysis will be assessed and alternate parameterisations will be considered where appropriate.

## 5.4 Subgroup Analyses

We will conduct the following subgroup analyses to assess if the intervention effect is statistically different between these groups.

- Ethnicity
- Gender
- Age < 60 & ≥ 60 years

- ISWT: High risk < 420 & Low risk ≥ 420

- Cardiac condition (MI, Angina or ACS)

The main analysis for each subgroup will involve using the same analytic principles as the primary analysis, but stratifying by the subgroup to estimate the mean difference in average daily physical activity when compared to the control group. Further subgroup analyses will investigate the interaction effects between the treatment and subgroup, this will include an

v 1.0

Date:

20/03/2019

additional interaction term to the model; 'subgroup x treatment'. Subgroup results will be graphically presented as forest plots, with the estimated difference of average daily physical activity between treatment groups with 95% confidence interval for the interaction.

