#### Aerobic fitness:

Incremental Shuttle walk test (metres) - as part of the ISWT blood pressure, heart rate, oxygen saturation, rating of perceived exertion and breathlessness will be obtained.

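### Section 5.4 tests effect modification by age and ISWT only through two-group cuts; if the effect changes roughly linearly with a roughly normal modifier, continuous interaction terms would keep information that the cuts discard

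*SAP*

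**What the plan says.** Section 5.4 of the SAP names five subgroup factors. Two of them are cuts of finer measurements: "Age < 60 & ≥ 60 years" and "ISWT: High risk < 420 & Low risk ≥ 420". The purpose given is "to assess if the intervention effect is statistically different between these groups".

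The main subgroup analysis repeats the primary model within each group. After that, "Further subgroup analyses will investigate the interaction effects between the treatment and subgroup", by adding the product of subgroup and treatment to the model. For age and ISWT the subgroup is the two-level category, so the test runs on the split variable. The results, with a 95% CI for the interaction, go on a forest plot.

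No other section supplies a continuous version of either test:

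- Section 5.2.2.3 covers interactions with gender and ethnicity only.
- The sentence in section 5.3 about alternate parameterisations concerns secondary endpoints.
- Section 2.2 lists the ISWT in metres, and a cut at 60 years presupposes age in years, so finer values are available.
- The only reason offered for either cut point is the high-risk and low-risk label on the ISWT groups.

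**The concern.** A two-group cut treats everyone on one side as alike, and treats people just either side of it as different. If the intervention effect shifts gradually with age or fitness, the variation within each group carries information about that shift, and the planned test does not use it. A risk label is a good reason to display results by group. It does not require the interaction test to rest on the groups alone.

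The trial is sized for the main effect, so any interaction test starts with little power. Weakening it further makes a non-significant result more likely when the effect does vary, and such a result is easily read as evidence that the programme works equally well at all ages and fitness levels. What is at stake is the interpretation of secondary, pre-specified analyses, not the primary comparison.

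**Working it through.** **Inputs from the SAP.** Section 1.2.6: target difference 2.1 mg; "assuming a standard deviation of 5.3 mg"; 80% power; 5% significance; 202 evaluable; 290 recruited. Section 1.2.2: 1:1 allocation. Section 4.1: two-sided tests at 0.05.

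**Reproducing the sample size.** A two-sample t-test with 2.1 mg, SD 5.3 mg, 80% power and two-sided 5% needs 100.96 per arm, that is 101 per arm or 202 in total, as stated. Then 202/(1 − 0.30) = 288.6, close to the stated 290. The inputs are therefore usable, and N = 202 is taken below.

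**Assumptions not in the SAP.** The modifier is roughly normal, the effect changes linearly with it, and the share of participants on one side of the cut is p. The SAP gives no distribution for age or ISWT, so a range of p is shown. The SD of 5.3 mg is used as the residual SD.

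**Information kept by the cut.** Relative efficiency of the two-group interaction test against the linear one:

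RE = φ(z_p)² / [p(1 − p)]

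At p = 0.5: 0.3989²/0.25 = 0.637. At p = 0.8: 0.2800²/0.16 = 0.490.

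| Split | RE | Information lost | Effective N of 202 |
|---|---|---|---|
| 50/50 | 0.637 | 36% | 129 |
| 60/40 | 0.622 | 38% | 126 |
| 70/30 | 0.576 | 42% | 116 |
| 80/20 | 0.490 | 51% | 99 |
| 90/10 | 0.342 | 66% | 69 |

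**Power in a worked example.** Take a linear modifier whose median-split difference equals the whole target effect of 2.1 mg. For a normal modifier the two halves differ by 2φ(0)/0.5 = 1.596 SD, so the slope is 2.1/1.596 = 1.32 mg per SD.

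- Continuous term: SE = 2 × 5.3/√202 = 0.746; 1.316/0.746 = 1.76; power = Φ(1.76 − 1.96) = 42%.
- Two-group term: SE = 5.3 × √[4/(202p) + 4/(202(1 − p))].

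| Split | Difference between groups (mg) | SE (mg) | Power |
|---|---|---|---|
| 50/50 | 2.10 | 1.49 | 29% |
| 70/30 | 2.18 | 1.63 | 27% |
| 80/20 | 2.30 | 1.86 | 24% |

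With a slope twice as steep, power is 94% for the continuous term against 80%, 76% and 70%.

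**Simulation check** (4,000 replicates, N = 202, slope 1.32 mg per SD). At 50/50, power was 42% continuous and 29% split, with relative efficiency 0.62. At 80/20 it was 42% and 23%, with relative efficiency 0.50. These agree with the formulae.

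**Sensitivity to the assumptions.**

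- Uniform modifier: loss of 25% at 50/50, rising to 52% at 80/20.
- Gamma-skewed modifiers (shape 4 and 9): loss of about 36% to 66%, for cuts from the 20th to the 80th percentile.
- A true step of 4.2 mg at the median: the two-group test had 80% power and the linear test 60%. Here the cut loses nothing and does better.

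**The case against.** The strongest reply is that section 5.4 asks whether the effect differs between named groups, and a group-by-treatment interaction answers exactly that. The cuts are pre-specified, so they neither bias the test nor inflate its type I error, and the planned 95% CI for the interaction will show how imprecise it is. All of this stands. The SAP is not in error here. The point is that it stops at the group question when the data can also address, more efficiently under a gradual change, whether the effect varies with age or fitness.

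Three stronger readings are tempting, and the document does not support them.

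- A reader might infer that the cuts throw away a third to a half of the information as a matter of fact. That range needs a near-normal modifier, a linear change in effect and a split between 50/50 and 80/20. The SAP states none of these. Normality is doubtful for ISWT in particular, because sections 1.2.4 and 1.2.5 admit only those at level three or above, which cuts off the lower tail.
- A reader might infer that continuous terms would make these tests adequately powered. They would not. At N = 202, 80% power needs a slope of about 2.80 × 0.746 = 2.1 mg per SD, so the effect would have to change by the whole target difference for every SD of age or ISWT.
- A reader might infer that keeping the grouped forest plot lets one judge whether a linear interaction fits. Two estimates per modifier always lie on a line, so it cannot.

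**Conclusion.** The point holds as an inexpensive improvement of minor importance. Basing the age and ISWT interaction tests only on two-group cuts costs about 36% of the information at 50/50 and about 51% at 80/20. This is conditional on a roughly normal modifier and a roughly linear change in effect, and on split proportions that the SAP does not give. The cost can be as low as 25% with a uniform modifier at 50/50, is larger for very uneven splits, and vanishes if the effect steps at the cut.

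In the worked example the gain is from 24–29% power to about 42%. That is a real gain, but a non-significant result would still be weak evidence of a uniform effect, because the trial is sized for the main effect. The primary analysis in section 5.2.1 and its conclusion are unaffected.

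**What to change.** Amend section 5.4 as follows:

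- For age and for baseline ISWT distance, test effect modification with the measure as a continuous term: its main effect plus its product with treatment, added to the primary model.
- Report each interaction estimate with its 95% CI, per stated unit of the modifier.
- Add one simple check for non-linearity of the interaction, such as a quadratic or spline term, and say in advance how it will be reported.
- Keep the pre-specified two-group estimates and their interaction CIs for the forest plot.
- Describe the interaction tests as exploratory and not powered.

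The cost is a few lines of SAP text and a few extra model terms, on data already being collected. The downside is the linearity assumption, which the added non-linear term is there to check.

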# 4 General Issues for Statistical Analysis

# 4.1 Multiplicity, Multiple Comparisons and Interim Analyses

All tests and reported p-values will be two-sided, where a p-value of < 0.05 will be considered to be statistically significant. Estimates will be presented with 95% confidence intervals. There will be no formal adjustment for multiple significance testing. The outcomes however, are clearly categorised by the degree of importance (primary and secondary). No formal interim analyses were planned.

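### SAP sections 5.2.2.3 and 5.4 give inconsistent subgroup rules for gender and ethnicity, and 5.4 ranks the stratum models above the interaction that answers its own question

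*SAP*

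**What the plan says.** Two parts of the SAP govern subgroup work on the primary outcome.

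- **Section 5.2.2.3**, under Sensitivity Analyses, fits interactions of arm with gender and with ethnicity, and continues: "If the interaction term is statistically significant at the 10% level then stratified analyses will be performed for that factor". The stratified models are those of the primary analysis.
- **Section 5.4** lists ethnicity, gender, age (below 60, 60 and over), ISWT (below 420, 420 and over) and cardiac condition (three categories). Its purpose is "to assess if the intervention effect is statistically different between these groups". It then says: "The main analysis for each subgroup will involve using the same analytic principles as the primary analysis, but stratifying by the subgroup". The interaction comes after that: "Further subgroup analyses will investigate the interaction effects between the treatment and subgroup". Section 5.4 gives no significance level for it. The results go into forest plots, "with the estimated difference of average daily physical activity between treatment groups with 95% confidence interval for the interaction".

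Section 4.1 sets a general rule for all tests, "where a p-value of < 0.05 will be considered to be statistically significant", with no multiplicity adjustment.

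**The concern.** Gender and ethnicity fall under both sections, with the same outcome and the same underlying model, but the rules differ in three ways: whether stratification is conditional, whether the interaction or the stratified analysis comes first, and which level the interaction is judged at (10%, or 5% by default). No sentence says which section governs. An analyst could settle that after seeing the data, which is what a SAP is meant to prevent.

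The ranking inside 5.4 is a separate matter. Separate models within strata say how large the effect is in each stratum and how precisely it is known. They do not test whether the effects differ; the interaction does. If the stratum models are the main analysis, a report may compare their significance and conclude that the programme works in one group and not in another when the true effects are equal.

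The plot sentence adds a smaller problem. A confidence interval for an interaction describes a difference between two treatment differences, so it is not the interval of a treatment difference within a subgroup.

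**Working it through.** **1. The two rules side by side, for gender and ethnicity**

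| | Section 5.2.2.3 | Section 5.4 |
|---|---|---|
| First step | Interaction | Stratified models |
| Stratified models run | When the interaction is significant at 10% | Always |
| Role of the interaction | Trigger | Further analysis |
| Level for the interaction | 10% | None given; 5% through section 4.1 |

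If the gender interaction had p = 0.30, section 5.2.2.3 would not call for stratified results and section 5.4 would. If it had p = 0.07, it would be significant under 5.2.2.3 and not under 5.4 with 4.1. With no true interaction, p falls between 0.05 and 0.10 with probability 0.05 per factor. For at least one of the two factors that is 1 − 0.95² = 0.0975, about 10%, if the tests are independent.

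**2. The SAP's own sample size**

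Inputs from section 1.2.6: difference 2.1 mg, SD 5.3 mg, two-sided 5%, power 80%. With n per arm, the standard error is 5.3 × √(2/n) and the noncentrality is 2.1 divided by it. At n = 101 the standard error is 0.746, the noncentrality 2.816 and the t-test power 0.800. That gives 202 in total, as stated.

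**3. What comparing stratum significance would do**

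Assume the same true effect of 2.1 mg in both strata, equal arms within strata and 202 evaluable participants. The SAP gives no subgroup shares, so the splits are assumed. With powers p1 and p2 in the two independent strata, the chance that exactly one is significant at 5% is p1(1 − p2) + p2(1 − p1).

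| Split | n per arm in each stratum | Power in each stratum | Exactly one significant |
|---|---|---|---|
| 50/50 | 50.5 and 50.5 | 0.505 and 0.505 | 2 × 0.505 × 0.495 = 0.50 |
| 30/70 | 30.3 and 70.7 | 0.329 and 0.648 | 0.329 × 0.352 + 0.648 × 0.671 = 0.55 |
| 20/80 | 20.2 and 80.8 | 0.233 and 0.707 | 0.233 × 0.293 + 0.707 × 0.767 = 0.61 |

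Under equal effects the interaction test gives a false signal only at its own level, 5% or 10%.

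**4. What the interaction can detect**

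The standard error of the interaction is √(SE1² + SE2²). For a 50/50 split this is √(1.055² + 1.055²) = 1.49. If the two effects truly differed by 2.1 mg, the ratio would be 2.1/1.49 = 1.41. By the normal approximation, power is Φ(1.41 − 1.96) = 0.29 at the 5% level and Φ(1.41 − 1.645) = 0.41 at 10%. For a 20/80 split the standard error is 1.86 and the powers are 0.20 and 0.30. The choice of level therefore matters, and a non-significant interaction is weak evidence that effects are equal.

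**5. Number of subgroup estimates**

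Section 5.4 yields 2 + 2 + 2 + 2 + 3 = 11 subgroup estimates.

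**The case against.** Several stronger readings are tempting, and the text does not carry them.

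- *A reader might infer that the two sections cannot both be followed.* Section 5.2.2.3 says when stratified analyses will be done; it does not say they are done only then. Someone who stratifies always, as 5.4 asks, also meets 5.2.2.3. A flat contradiction needs an implied 'only if', which is natural but is an inference. What stands is that the condition in 5.2.2.3 has no function beside 5.4, and that the levels differ.
- *A reader might infer that 5.4 has no valid test of effect differences.* It has one: the interaction is planned for all five factors. The fault is its rank and the level left unstated.
- *A reader might count 11 planned significance tests.* Section 5.4 stratifies in order to estimate mean differences and mentions no p-values within subgroups. There are 11 planned estimates, and showing them in a forest plot is normal practice. Nothing in the SAP marks them as descriptive, however, and the general rule in 4.1 covers every test reported.
- *A reader might take 50% to 61% as an error rate of the planned analysis.* It measures a misreading of stratified results that the SAP does not prescribe. It also ignores the planned adjustment for baseline activity.
- *A reader might conclude that a wrong interval will be plotted.* The clause could mean subgroup intervals taken from the interaction model, or the interaction shown beside the estimates. It is unclear and needs rewording; it does not prove that the plot will be wrong.

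It can also be said that 5.2.2.3 is only a sensitivity analysis. It uses the same factors, outcome and model, so the label does not reconcile the rules.

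**Conclusion.** The point holds in this form: the rules for gender and ethnicity are inconsistent in condition, order and significance level; section 5.4 gives the leading place to stratum models although its aim is answered by the interaction it ranks second; and the plot sentence attaches an interval to the wrong quantity, or at best leaves this open.

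The illustration shows why the ranking matters. With identical effects, reading significance stratum by stratum would suggest a difference in about half of trials or more (50% to 61% over the assumed splits). It rests on assumed subgroup shares, an unadjusted t-test, 202 evaluable participants and a true effect of 2.1 mg with SD 5.3 mg in every stratum.

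The change should be made, but the matter is moderate: it concerns subgroup inference and presentation, and the primary analysis and its result are untouched.

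**What to change.** 1. Delete section 5.2.2.3, or replace it with a cross-reference to 5.4.
2. In 5.4, name the treatment-by-subgroup interaction, from the primary model fitted to the full sample, as the inferential result for each of the five factors. State one significance level for all of them. For cardiac condition, with three categories, say that this is one joint test.
3. Always show the 11 subgroup estimates, whatever the interaction result, and call them descriptive.
4. Reword the forest plot sentence so that each subgroup estimate carries its own 95% CI, with the interaction p-value beside each factor.

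The cost is a change of SAP wording. No new data are needed, and the analysis work is the same or slightly less.

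### As worded, section 5.4 puts the interaction's 95% confidence interval on the treatment differences plotted for each subgroup, which are a different parameter

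*SAP*

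**What the plan says.** SAP section 5.4 lists five subgroup factors: ethnicity, gender, age, ISWT and cardiac condition. The first four have two levels. Cardiac condition has three (MI, angina, ACS).

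The section then sets out two steps. The main analysis for each factor applies the primary-analysis approach, "stratifying by the subgroup to estimate the mean difference in average daily physical activity when compared to the control group". After that, "Further subgroup analyses will investigate the interaction effects between the treatment and subgroup", by adding an interaction term to the model.

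The last sentence describes the display. Results will appear as forest plots "with the estimated difference of average daily physical activity between treatment groups with 95% confidence interval for the interaction". Section 5.4 does not otherwise say which interval goes with each plotted difference, and it does not give the interaction a row or column of its own.

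Section 4.1 has a general rule: "Estimates will be presented with 95% confidence intervals".

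**The concern.** The plotted estimate comes from the first step and the interval from the second. They refer to different parameters with different null hypotheses. For a level's own difference, the null is that the intervention has no effect in that level. For the interaction, the null is that the effect is the same in every level.

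A reader of a forest plot takes each bar to show the uncertainty of the point it is drawn on. If the interaction's width is drawn around a level's difference, the estimate looks less precise than it is. If the interaction interval is drawn where it is actually centred, the bar shows a difference of differences beside a label that promises a treatment difference. A bar that spans zero is then the expected result when the intervention works equally well in both levels, yet it could be read as no effect in that subgroup.

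The forest plot is the only presentation that section 5.4 names for its subgroup results.

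**Working it through.** **Inputs**
- Difference 2.1 mg, SD 5.3 mg, 80% power, two-sided 5%, 202 analysed (SAP section 1.2.6; two-sided 0.05 also in section 4.1).
- Allocation 1:1 (section 1.2.2).
- Subgroup level sizes: not in the SAP, so a range is assumed.
- Also assumed: equal arms within each level, the same SD in both levels, and no reduction of the SD by covariates.

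**The plan's own figure.** Normal approximation: n per arm = 2(1.96 + 0.8416)² × 5.3² / 2.1² = 99.99, so 100 per arm and 200 in total. With the noncentral t distribution, 101 per arm gives power 0.8002, so 202 in total. The stated 202 is reproduced.

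**Formulas**
- Standard error of the difference in a level of size n: SE = √(SD²/(n/2) + SD²/(n/2)) = 2·SD/√n.
- Separate fits by level are independent, so SE(interaction) = √(SE₁² + SE₂²). This always exceeds either SE on its own.
- For a level holding a fraction p of participants, the ratio of the interaction interval's width to the level's own is √(1 + p/(1−p)) = 1/√(1−p). The SD cancels.

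**50/50 split (101 per level)**
- Own SE = 10.6/√101 = 1.055; half-width 1.96 × 1.055 = 2.07 mg.
- Interaction SE = 1.055 × √2 = 1.492; half-width 2.92 mg; ratio 1.41.
- Coverage of the level's difference with the wider bar: 2Φ(1.96 × 1.414) − 1 = 99.4%.
- With a true effect of 2.1 mg, the chance that the bar excludes zero is 51% with the level's own interval and 22% with the interaction's width.

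**Other splits (half-widths in mg)**

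| Split | Larger level, own | Smaller level, own | Interaction | Ratio, larger | Ratio, smaller |
|---|---|---|---|---|---|
| 50/50 | 2.07 | 2.07 | 2.92 | 1.41 | 1.41 |
| 60/40 | 1.89 | 2.31 | 2.98 | 1.58 | 1.29 |
| 70/30 | 1.75 | 2.67 | 3.19 | 1.83 | 1.20 |
| 80/20 | 1.63 | 3.27 | 3.65 | 2.24 | 1.12 |
| 90/10 | 1.54 | 4.62 | 4.87 | 3.16 | 1.05 |

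At 80/20, the chance of excluding zero falls from 71% to about 3% in the larger level, and from 24% to 18% in the smaller one.

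**Centring.** Suppose the estimate is 2.1 mg in both halves of 202. Each level's own interval is 2.1 ± 2.07, or 0.03 to 4.17. The interaction interval is 0 ± 2.92, or −2.92 to 2.92, which does not refer to the plotted 2.1. Its width moved onto 2.1 gives −0.82 to 5.02.

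**Cardiac condition.** Three levels give three plotted differences but 3 − 1 = 2 interaction coefficients. One interaction interval per row cannot be produced, and there is no single interval for the factor.

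**The case against.** The strongest reply is that the sentence is compressed drafting. Its second *with* could introduce a further item, so that the differences are plotted and the interaction interval is reported as well. It could also mean intervals taken from the interaction model. The general rule in section 4.1 would then supply each level's own interval. The impossibility for cardiac condition points the same way: whoever programs the plot would have to stop and ask. This is a fair account of what may have been intended. It does not remove the point, because the specific sentence names a specific interval, the general rule does not clearly override it, and two programmers could draw different figures from it.

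A reader might also infer that conclusions about who benefits would be wrong under either way of drawing the bars. The SAP does not support that. Section 5.4 opens by asking whether the intervention effect differs between groups, and the interaction interval is the one that answers this. Centred on the interaction coefficient, it should exclude zero only about 5% of the time when effects are equal, which is correct behaviour for that question. The fall from 51% to 22% concerns significance within a level, which is not the section's stated aim.

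Nor would the bars around a level's difference under-cover. They would over-cover, at about 99.4% for a 50/50 split.

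Finally, the figures in mg and the exclusion probabilities rest on assumed level sizes and an unadjusted SD, whereas the model in section 5.2.1 adjusts for baseline activity and change in wear time. The width ratios do not depend on the SD, provided it is the same in both levels.

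**Conclusion.** The point stands as a wrongly stated display rule. Read as written, section 5.4 attaches to each plotted difference the interval of another parameter. With separate stratified fits, that interval is wider than the level's own for any split: 1.41 times at 50/50, and up to 3.16 times for the larger level at 90/10. Alternatively, it is centred on the difference of differences. In a model with covariate effects shared across levels, the width relation is approximate but the mismatch of parameters remains.

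The harm is conditional on the sentence being programmed literally. It is limited to the presentation of subgroup results and does not touch the primary analysis, the sample size or the interaction tests. It would be going too far to say that the trial is set to draw wrong conclusions about subgroups.

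**What to change.** Replace the last sentence of section 5.4 with:

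> Forest plots will show, for each subgroup level, the estimated intervention-minus-control difference from the main (stratified) subgroup analysis with its own 95% CI. The interaction will be reported separately for each factor: estimate, 95% CI and p-value for two-level factors, and a joint 2-df test for cardiac condition.

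This keeps the stratified fits as the main subgroup analysis. Taking the level differences from the interaction model instead would be a change of method that the defect does not require.

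The cost is one sentence of SAP wording. The stratified fits already yield the intervals, the interaction models are already planned, and the joint test is one further command. No new data or participants are needed. Section 1 allows the SAP to be amended and has it finalised before database lock, so the change belongs there.
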